# 10.4 Discontinued Subjects

Discontinued subjects are those who withdraw or are withdrawn from the study after Visit 1. Subjects may discontinue from the study at any time for any reason. Subjects may also be discontinued from the study at any time if, in the opinion of the Investigator, their continued participation poses a risk to their health. Discontinued subjects will not be replaced (ie, their subject numbers will not be re-assigned/re-used).

Should a subject exhibit any clinically relevant signs, symptoms, or other clinical observations that possibly could be associated with suspected sensitivity or intolerance to one of the IPs, the Investigator must document those observations on an AE form.

Any subject who exits early from the study must undergo all procedures outlined at Visit 3. Additionally, the Exit form must be completed and the reason for discontinuation must be identified.

Finally, to ensure the safety of all subjects who discontinue early, Investigators should assess each subject and, if necessary, advise them of any therapies and/or medical procedures that might be needed to maintain their health.

Document: TDOC-0053461 Version: 1.0; CURRENT; Most-Recent; Effective

Status: Effective Page 40 of 54

#### 10.5 Clinical Study Termination

If the clinical study is prematurely terminated or suspended, the Sponsor will inform the Investigator and the regulatory authorities of the termination/suspension and the reason(s) for the termination/suspension. The Investigator should promptly notify the IEC/IRB of the termination or suspension and of the reasons. The Sponsor reserves the right to close the investigational site or terminate the study in its entirety at any time, for reasonable cause. Reasons for the closure of an investigational site or termination of a study may include:

- Successful completion of the study
- The study's enrollment goals are met
- The Investigator fails to comply with the protocol or GCP guidelines
- Safety concerns
- Sufficient data suggesting lack of effectiveness
- Inadequate recruitment of subjects by the Investigator

The Investigator also may terminate the study at his/her site for reasonable cause. If the Sponsor terminates the study for safety reasons, it will immediately notify the Investigator(s) by telephone and subsequently will provide written confirmation of and instructions for study termination.

Document: TDOC-0053461 Version: 1.0; CURRENT; Most-Recent; Effective

Status: Effective Page 41 of 54

#### 11 ANALYSIS PLAN

Continuous variables will be summarized using the number of observations, mean, standard deviation, median, minimum and maximum, as well as confidence intervals or confidence limits where applicable. Categorical variables will be summarized with counts and percentages from each category. Any deviations to this analysis plan will be updated during the course of the study as part of a protocol amendment or will be detailed in the clinical study report.

## 11.1 Subject Evaluability

The final subject evaluability will be determined prior to breaking the code for the assignment of fitting guide and/or lens and locking the database, based upon the DEP.

#### 11.2 Analysis Data Sets

#### 11.2.1 Safety Analysis Set

Safety analyses will be conducted using the safety analysis set on a treatment-emergent basis. As such, the safety analysis set will include all subjects/eyes exposed to study lenses evaluated in this study, except for the trial lenses used for parameterization and fitting at Visit 1. For treatment-emergent safety analyses, subjects/eyes will be categorized under the actual study lenses exposed.

# 11.2.2 Full Analysis Set

The FAS will include:

- all randomized subjects to AOA MF or DACP MF as well as subjects assigned to DT1 MF and
- 2. who are exposed to study lenses including those used for parametrization and fitting at Visit 1.

# 11.2.3 Per Protocol Analysis Set

The PP analysis set will include:

- all randomized subjects to AOA MF or DACP MF as well as subjects assigned to DT1 MF and
- 2. all data/subjects which have not met any of the critical deviation or non-evaluable criteria identified in the DEP.

Document: TDOC-0053461 Version: 1.0; CURRENT; Most-Recent; Effective

Status: Effective Page 42 of 54

## 11.3 Demographic and Baseline Characteristics

Demographic information (age, sex, ethnicity, race) will be summarized on the safety, full, and PP analysis sets. Baseline characteristics on habitual lens

will be

summarized on the full and PP analysis sets.

## 11.4 Effectiveness Analyses

This study defines one primary endpoint,

All effectiveness evaluations will use the FAS as the primary analysis set. Supportive analyses of the primary

effectiveness endpoint will be conducted using the PP analysis set only if the number of subjects excluded from PP analysis set exceeds 5% of FAS.

For all planned inferential analyses, alternative models/methods may be considered if convergence cannot be achieved.

# 11.4.1 Primary Effectiveness

The primary objective of this study is to demonstrate noninferiority of the alternative fitting guide when compared to the current fitting guide in fitting.

The corresponding endpoint is the number of trial lenses needed to fit each eye at the Screening/Fitting visit (Visit 1), derived from the number of on-eye lens prescriptions.

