## 10 STUDY PROCEDURES

## 10.1 Outline of Study

This is a multicenter, subject-masked, randomized, parallel, stratified, active-controlled evaluation to compare the fitting success (determined by the mean number of trial lenses needed to successfully fit each eye) using the current MF fitting guide compared to the alternative MF fitting guide for all three of the Alcon MF contact lenses (AOA MF, DACP MF, and DT1 MF).

Approximately 180 subjects will be enrolled at approximately 20 sites, with approximately 9 subjects enrolled per site. To participate in the study, subjects must be current soft contact lens wearers needing presbyopia-correction, with a near spectacle ADD of +0.50 D to +2.50 D (inclusive).

The expected duration of subject participation in the study is  $10 \pm 3$  days (7 days minimum) and up to 33 days (maximum) for all subjects with a minimum of 2 scheduled visits, up to 5 scheduled visits, depending on necessity of refit dispensing and follow-up visits.

Document: TDOC-0053461 Version: 1.0; CURRENT; Most-Recent; Effective

Status: Effective Page 32 of 54

Figure 10–1 **Study Design** Visit 1 Screening / Fitting Visit 0-7 Days Visit 2 Dispense 1 **MF Contact Lens Dispensing Visit** 10 ± 3 days Visit 3 Follow Up 1 NO Yes-Prescription optimization required? Visit 2 Dispense 2 **Visit 3 Exit** Repeat Visit 2 procedures and **Exit Subject** dispense new study lenses 10 ± 3 days **Visit 3 Exit Exit Subject** Prescription optimization required? YES Assess optimal prescription and **Exit Subject** 

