### 10.2 Visits and Examinations

## 10.2.1 General Summary of Study Visits

The general study design dictates that subjects will be screened and their eligibility confirmed at Visit 1. Subjects who are qualified to participate in the study will have their lens parameters optimized and their prescription determined at Visit 1 based upon the fitting guide assigned to the site prior to site activation.

Document: TDOC-0053461 Version: 1.0; CURRENT; Most-Recent; Effective

Status: Effective Page 33 of 54

Study lenses from the fitting set may be dispensed to the subject at Visit 1 if a sufficient number of lenses are available in the noted prescription. Otherwise, study lenses may be ordered for dispensing to subject at 'Visit 2 Dispense 1'.

For Visit 2 Dispense 1, subjects will return to the site 0-7 days from Visit 1 at which time study lenses will be dispensed based upon the prescription determined at Visit 1. A series of ophthalmic assessments will be conducted on the subjects with study lenses inserted,

Subjects will be scheduled to return to the site for their 'Visit 3 Follow-up 1' after  $10 \pm 3$  days of lens wear in study lenses.

A series of ophthalmic examinations will be conducted on the subject at Visit 3, and their optimal prescription assessed.

- If the subject is determined to have a successful fit following the optimal prescription assessment, the subject may be exited from the study. In this case, Visit 3 Follow-up 1 will function as Visit 3 Exit.
- If the subject is determined NOT to have a successful fit, and requires a new
  prescription, the subject is to be refit based upon the fitting guide assigned to the site.
  A new pair of study lenses will be dispensed.

For subjects who do NOT exit at Visit 3, 'Visit 3 Follow-up 1' will function as 'Visit 2 Dispense 2'. Repeat the procedures conducted at Visit 2 on the subject and dispense a new pair of study lenses with the new prescription. Schedule the subject to return to the site for 'Visit 3 Exit' after  $10 \pm 3$  days of lens wear in study lenses

For Visit 3 Exit, conduct the same ophthalmic assessments that were conducted for the subject's Visit 3 Follow-up 1,

Assess the subject's optimal prescription following completion of ophthalmic assessments.

- If the subject is determined to have a successful fit following the optimal prescription assessment, the subject may be exited from the study.

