- If the subject is determined NOT to have a successful fit with the re-dispensed lenses,
  a re-assessment of optimal prescription is to be conducted on the subject. However, no
  additional lenses are to be dispensed following the re-assessment of prescription. The
  subject is then exited from the study and considered NOT to have had a successful fit.

Document: TDOC-0053461 Version: 1.0; CURRENT; Most-Recent; Effective

Status: Effective Page 34 of 54

[figure not shown]

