# 11.4.1.1 Statistical Hypotheses

The null and alternative hypotheses are formulated as follows:

$$H_0:\, \mu_{(AFG)} - \mu_{(CFG)} \geq 0.5$$

$$H_a$$
:  $\mu_{(AFG)} - \mu_{(CFG)} < 0.5$ 

where  $\mu_{(AFG)}$  and  $\mu_{(CFG)}$  denote the mean number of trial lenses used to achieve fit in each eye using the alternative and current fitting guide, respectively, at the Screening/ Fitting visit. All Alcon MF lenses are to be included.

Document: TDOC-0053461 Version: 1.0; CURRENT; Most-Recent; Effective

Status: Effective Page 43 of 54

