#### 11.4.1.2 Analysis Methods

A mixed effect repeated measures model will be utilized to test these hypotheses, including terms for fitting guide,

Correlation between eyes will be accounted for in this analysis.

Fitting guide difference (Alternative minus Current) and the corresponding one-sided 95% upper confidence limit (UCL) will be computed. Noninferiority in fitting will be declared if UCL < 0.5 at Visit 1.

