# 11.10 Sample Size Justification

Sample size calculation for the primary effectiveness hypothesis on fit success is based upon results With an assumed common standard deviation of 0.6 and expected difference of 0.25, a sample size of 80 (160 eyes) in each group will provide 83% power for a noninferiority margin of 0.5, at one-sided  $\alpha$ =0.05, based upon a two group t-test.

Document: TDOC-0053461 Version: 1.0; CURRENT; Most-Recent; Effective

Status: Effective Page 47 of 54

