Short Title:

**Statistical Analysis Plan
CLK027-P001**

Full Title:

**Statistical Analysis Plan
CLK027-P001 / NCT03118934**

Protocol Title: Assessing Fitting Guides in Alcon Multifocal Contact Lenses

Project Number: CLK027-P001

Reference Number:

Protocol TDOC Number: TDOC-0053461

Author:

[REDACTED]

[REDACTED]

Template Version: Version 4.0, approved 16MAR2015

Approvals: See last page for electronic approvals.

Job Notes:

This is the first revision (Version 2.0) Statistical Analysis Plan for this study. This version of the Statistical Analysis Plan is based on Version 1.0 of the study protocol.

Executive Summary:

Key Objectives:

To demonstrate noninferiority of the alternative fitting guide compared to the current fitting guide as determined by the mean number of trial lenses needed to fit each eye at the Screening/Fitting visit for all Alcon multifocal (MF) lenses combined

Decision Criteria for Study Success:

Success of this study will be based on demonstration of noninferior mean number of trial lenses needed to fit each eye of the alternative fitting guide compared to the current fitting guide, at Screening/Fitting visit for all Alcon MF lenses combined.

Table of Contents

Statistical Analysis Plan CLK027-P001 1

Table of Contents 3

List of Tables 4

List of Figures 4

1 Study Objectives and Design 5

1.1 Study Objectives 5

1.2 Study Description 6

1.3 Randomization 7

1.4 Masking 8

1.5 Interim Analysis 8

2 Analysis Sets 8

2.1 Safety Analysis Set 8

2.2 Full Analysis Set 8

2.3 Per Protocol Analysis Set 8

3 Subject Characteristics and Study Conduct Summaries 9

4 Effectiveness Analysis Strategy 9

4.1 Effectiveness Endpoints 10

4.2 Effectiveness Hypotheses 11

4.2.1 Hypothesis for the Primary Endpoint 11

█ 11

4.3 Statistical Methods for Effectiveness Analyses 11

4.3.1 Primary Effectiveness Analyses 11

█ 12

4.4 Multiplicity Strategy 15

█ 15

4.6 Interim Analysis for Effectiveness 15

5 Safety Analysis Strategy 15

5.1 Safety Endpoints 15

5.2 Safety Hypotheses 15

5.3 Statistical Methods for Safety Analyses 15

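### Does the primary trial-lens count need to change because successful fit is judged only at Visit 3, so that refits and failed fits score like first-time fits?

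*Protocol*

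**What the plan says.** The formal definition is in Protocol 11.4.1 and is repeated in SAP 4.1. It reads: "the number of trial lenses needed to fit each eye at the Screening/Fitting visit (Visit 1), derived from the number of on-eye lens prescriptions". The hypotheses in Protocol 11.4.1.1 concern "the mean number of trial lenses used to achieve fit in each eye using the alternative and current fitting guide", and that sentence ends by restricting the means to the Screening/Fitting visit. The decision rule in 11.4.1.2 is "Noninferiority in fitting will be declared if UCL < 0.5 at Visit 1". The SAP Executive Summary opens its success criterion with "Success of this study will be based on demonstration of noninferior mean number of trial lenses needed to fit each eye" and closes it with the same restriction to the Screening/Fitting visit.

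The descriptive text is looser. Protocol 10.1 (repeated in SAP 1.2) speaks of "fitting success (determined by the mean number of trial lenses needed to successfully fit each eye", and Protocol 11.10 calls the hypothesis the "primary effectiveness hypothesis on fit success".

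Protocol 10.2.1 sets out what happens after the fitting visit. At Visit 3 the optimal prescription is assessed. If the fit is not successful and a new prescription is required, "the subject is to be refit based upon the fitting guide assigned to the site", and new lenses are dispensed once. If the fit is still unsuccessful at Visit 3 Exit, the "subject is then exited from the study and considered NOT to have had a successful fit".

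**The concern.** Read together, these passages suggest that the primary count claims more than it measures. If success is settled at Visit 3, the number of lenses needed to reach it is not known at Visit 1, and for a subject who exits without a successful fit no such number exists. Both kinds of eye nevertheless enter the analysis at their Visit 1 count, and the refit prescription adds nothing.

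The stake would be the recommendation. Protocol 5.1 wants one global guide that saves practitioners' time and serves patients well. A guide that settles quickly at Visit 1 but brings more subjects back for a refit could be declared noninferior, while one that takes longer at Visit 1 and avoids refits would be penalised. Only the subjects are masked to the guide (Protocol 9.4, SAP 1.4), so the person fitting the lenses knows which guide is in use.

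**Working it through.** **Inputs.** Protocol 11.10 and SAP 7 give 80 subjects per group, common SD 0.6, expected difference 0.25, margin 0.5, one-sided α = 0.05 and a two-group t-test. The documents give no refit rate, so every refit figure below is an assumption. Site clustering is ignored, as in the plan's own calculation.

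**1. The plan's figure.** SE = 0.6 × √(2/80) = 0.0949. The distance to the margin is 0.5 − 0.25 = 0.25, so the noncentrality is 0.25/0.0949 = 2.635 on 158 degrees of freedom. Power is 83.6%, which agrees with the stated 83%. With t(0.95, 158) = 1.65455, the expected Visit 1 upper confidence limit (UCL) is 0.25 + 1.65455 × 0.0949 = 0.407. Refits do not enter it.

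**2. What refits could do to a total count.** Let pC and pA be the proportions of subjects refit under the current and alternative guides. Let m be the prescriptions added per eye for a refit subject (1 if both eyes change, 0.5 if one does), independent of the Visit 1 count, and let d be the true Visit 1 difference. Then

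- difference D = d + m(pA − pC)
- SE = √{[0.36 + m²pC(1 − pC) + 0.36 + m²pA(1 − pA)]/80}
- expected UCL = D + 1.65455 × SE

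With d = 0.25 and m = 1:

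| Refits of 80, current v alternative | D | SE | Expected UCL |
|---|---|---|---|
| 8 v 8 | 0.25 | √(0.90/80) = 0.1061 | 0.4255 |
| 8 v 13 | 0.3125 | 0.1087 | 0.492 |
| 8 v 14 | 0.325 | 0.1092 | 0.506 |
| 8 v 16 | 0.35 | √(0.97/80) = 0.1101 | 0.532 |
| 16 v 8 | 0.15 | 0.1101 | 0.332 |

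The expected UCL for total lenses first reaches 0.5 when the alternative guide has 7, 6 or 5 more refit subjects than the current guide, for 4, 8 or 16 current-guide refits respectively. If only one eye per refit subject changes (m = 0.5), the excess needed is 14 in each case. If the true Visit 1 difference is 0, it is 25 to 26 subjects with m = 1 and 54 with m = 0.5.

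**3. The cost of a second test.** Suppose total lenses were also tested against 0.5, and a plain noninferiority conclusion required both tests to pass. A simulation with normal Visit 1 counts, d = 0.25, SD 0.6, 80 per group and a 10% refit rate under both guides gives:

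- primary passes: 84%
- total-lens test passes: 76%
- both pass: 74%

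So in 84 − 74 = 10% of trials the conclusion would be weakened although the guides do not differ in refits. That is 10/84, about one in eight of the primary successes.

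**4. Would a total count repair the complaint?** Adding one for a refit gives an eye refit successfully and an eye refit and then exited as not fitted the same score, its Visit 1 count plus 1. A subject lost before Visit 3 gets no addition and looks like a success. The 0.5 margin was set for trial lenses at one visit, and nothing in the documents supports it for a sum over two visits.

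**5. The texts side by side.** In Protocol 10.2.1, Visit 1 is where lens parameters are optimised and the prescription is settled. Visit 3 asks whether that prescription still serves after about ten days of wear, and Figure 10-1 puts the question there as one of prescription optimisation. A lens accepted at Visit 1 and changed at Visit 3 was still a completed Visit 1 fitting. The count belongs to the first stage and the successful-fit status to the second.

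**The case for a change.** The strongest case for a change has three parts. First, study success rests on the Visit 1 count alone, and Protocol 11.4.2 defines no secondary effectiveness objective. Second, a refit costs practitioner time and is a poorer result for the patient, which are the two things Protocol 5.1 cares about. Third, an excess of 5 to 7 refit subjects out of 80 would carry the total-lens UCL past 0.5 while the primary limit stayed at 0.407. A supportive analysis agreed before unmasking would cost little.

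Some of this stands. Protocol 10.1 and SAP 1.2 are loosely worded, the count does not carry refits or final failures, and a reader of the trial report would want to see those numbers by guide.

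The rest does not lead to a change. The 5 to 7 figure needs a true Visit 1 difference of 0.25, both eyes changed and a real imbalance in refits, and the documents support none of these as a forecast. Much relevant text is also blacked out: Visit 1 procedure steps in Protocol 10.2.2.1, the testing order after the primary endpoint, and further endpoints and tables in the SAP. A Visit 1 acceptance criterion or an analysis of later fit success may be there, so it cannot be said that refits go unexamined. Dispense 2 exposure already defines the adverse event periods in SAP 5.3.1, so refit subjects should be identifiable for a descriptive count without an amendment.

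**Conclusion.** The observation is accurate, but the plan is sound for the question it sets. Every operative statement (objective, endpoint, hypotheses, decision rule, success criterion) is tied to the Screening/Fitting visit, and the derivation from on-eye prescriptions gives each trial-fitted eye a count. An analyst following the SAP would compute the right quantity, and the success criterion already phrases the conclusion as a mean number of trial lenses at that visit. The success label in Protocol 10.1 and SAP 1.2 is a slip of wording that changes no number.

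Counting lenses at the fitting visit is a fair choice for a study prompted by the time that fitting is thought to take. Replacing or gating it with a total count would borrow a margin set for another quantity, would still not separate failed fits from successful refits, and would lower the chance of a clean conclusion from about 84% to 74% with equal 10% refit rates. These figures rest on the plan's inputs, independent subjects and assumed refit rates. The direction of any real effect cannot be read from the documents.

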# 11.4.1.1 Statistical Hypotheses

The null and alternative hypotheses are formulated as follows:

$$H_0:\, \mu_{(AFG)} - \mu_{(CFG)} \geq 0.5$$

$$H_a$$
:  $\mu_{(AFG)} - \mu_{(CFG)} < 0.5$ 

where  $\mu_{(AFG)}$  and  $\mu_{(CFG)}$  denote the mean number of trial lenses used to achieve fit in each eye using the alternative and current fitting guide, respectively, at the Screening/ Fitting visit. All Alcon MF lenses are to be included.

Document: TDOC-0053461 Version: 1.0; CURRENT; Most-Recent; Effective

Status: Effective Page 43 of 54

#### 11.4.1.2 Analysis Methods

A mixed effect repeated measures model will be utilized to test these hypotheses, including terms for fitting guide,

Correlation between eyes will be accounted for in this analysis.

Fitting guide difference (Alternative minus Current) and the corresponding one-sided 95% upper confidence limit (UCL) will be computed. Noninferiority in fitting will be declared if UCL < 0.5 at Visit 1.

## 11.4.2 Secondary Effectiveness

No secondary effectiveness objective is defined for this study.

## 11.4.2.1 Statistical Hypotheses

Not applicable.

## 11.4.2.2 Analysis Methods

Not applicable.

Document: TDOC-0053461 Version: 1.0; CURRENT; Most-Recent; Effective

Status: Effective Page 44 of 54

Document: TDOC-0053461 Version: 1.0; CURRENT; Most-Recent; Effective

## 11.5 Handling of Missing Data

All data obtained in evaluable subjects/eyes will be included in the analysis. No imputation for missing values will be carried out for the effectiveness analysis.

# 11.6 Multiplicity

A sequential gatekeeping strategy will be implemented to control testing of multiple effectiveness endpoints. Therefore, the overall type I error will be controlled at one-sided 0.05 with the following testing order:

Noninferiority of primary endpoint

.

# 11.7 Safety Analysis

The safety endpoints for this study are AEs, biomicroscopy findings, and device deficiencies.

Descriptive summaries (counts and percentages) for ocular and nonocular AEs will be presented by Medical Dictionary for Regulatory Activities Preferred Terms. In addition to an overall presentation of AEs, reports will be generated for serious AEs. AEs leading to study discontinuation will be identified. Individual subject listings will be provided, as necessary.

Document: TDOC-0053461 Version: 1.0; CURRENT; Most-Recent; Effective

Status: Effective Page 46 of 54

Individual subject listings will be provided for AEs that occur after signing informed consent but prior to exposure to study lens not used for lens parametrization and fitting at Visit 1.

Each biomicroscopy parameter will be tabulated by its grade. For each biomicroscopy parameter, counts and percentages of eyes that experience an increase of  $\geq 2$  grades from baseline to any subsequent visit will be presented. Baseline is defined as Visit 2. A supportive listing will be generated which will include all biomicroscopy data from all visits for these eyes experiencing the increase.

Two listings (prior to exposure of study lenses not used for lens parametrization and fitting at Visit 1, and treatment-emergent) of device deficiencies will be provided. Additionally, each device deficiency category will be tabulated.

No inferential testing will be done for safety analysis.

